3.3 Study Population

This is a study in pediatric patients < 18 years of age with CLN2 disease. Key inclusion and exclusion criteria are as follows:

Inclusion Criteria

- Clinical assessment of the Hamburg motor-language aggregate score 3-6 at Screening

Exclusion Criteria

Another inherited neurologic disease, e.g., other forms of CLN or seizures unrelated to CLN2 disease (patients with febrile seizures may be eligible)

Another neurological illness that may have caused cognitive decline (e.g., trauma, meningitis, hemorrhage) or interfere with disease rating (autism) before Screening

Has received stem cell, gene therapy, or ERT

Episode of generalized motor status epilepticus within 4 weeks before the First Dose visit

Severe infection (e.g., pneumonia, pyelonephritis, or meningitis) within 4 weeks before the First Dose visit (enrollment may be postponed)

Has received any investigational medication within 30 days before the first infusion of study drug or is scheduled to receive any investigational drug other than BMN 190 during the course of the study

3.4 Study Dosage and Administration

BMN 190 is administered every 14 days from the date of the first infusion (± 3 days) for at least 144 weeks according to the subject's age:

- birth to < 6 months: 100 mg
- 6 months to < 1 year: 150 mg
- 1 year to < 2 years: 200 mg (first 4 doses), 300 mg (subsequent doses)
- ≥ 2 years: 300 mg

	BMN 190-203 Statistical Analysis Plan, Version 2.0	Pg. 13 of 53
---	---	--------------

3.5 Sample Size Determination

Sample size was determined on the basis of clinical judgment. Statistical power was not a consideration.

3.6 Blinding and Randomization Methods

This is a single-arm, open-label study; there is no blinding to treatment or randomization.

3.6.1 Interim Analysis

No formal interim analyses were planned. Analyses were produced for a biologics licensing application to FDA based on visits through November 01, 2016. Analyses were produced for purpose of regulatory reporting and congress presentations based on data through April, years 2018, 2019, 2020, and 2021. An interim clinical study report (CSR) based on visits up to 26 April 2020 was produced at the request of the European Medicines Agency Paediatric Committee. This interim report included safety and the following efficacy analyses:

- Summary statistics ML rate of decline
- Summary statistics ML rate of decline subset to baseline ML<6
- Summary statistics ML rate of decline subset to baseline ML=6
- Kaplan-Meier time to unreversed ML 2-point decline or score of zero
- Kaplan-Meier time to MLVS<12 for patients with baseline MLVS=12
- ML summary statistics by visit
- M, L, V (Vision), and S (Seizure) score summary statistics by visit
- MLV and MLVS (Motor-Language-Vision-Seizure) summary statistics by visit
- MRI parameter summary statistics by visit
- Immunogenicity
- Adverse events
- Clinical Laboratory Tests
- Vitals signs
- Electrocardiogram (ECG)
- Electroencephalograms (EEG)
- Neurological Examination

	BMN 190-203 Statistical Analysis Plan, Version 2.0	Pg. 14 of 53
---	---	--------------

- Cerebrospinal Fluid Surveillance (CSF)

The analyses of ML, MLVS, S also included matched analyses with natural history data.

There is no Data Monitoring Committee. However, BioMarin has convened a Data Review Board of internal and external experts to assist the Medical Monitor in assessing data.

Early stopping is to be considered based on clinical judgment; no inferential stopping rules are being employed.

Draft

	BMN 190-203 Statistical Analysis Plan, Version 2.0	Pg. 15 of 53
---	---	--------------

4 GENERAL ANALYSIS CONSIDERATION

Safety and efficacy variables will be summarized descriptively. Descriptive statistics include subject count, mean, median, standard deviation, minimum, and maximum for continuous variables and count and percentage for categorical variables. The 95% confidence interval for mean and percentiles may be included, if appropriate.

4.1.2 Safety

The Safety Analysis Population is defined as all subjects who had an ICV reservoir implanted.

4.1.3 Study 190-901 Evaluable Population

Study 190-901 is a natural history study of patients diagnosed with CLN2 disease. The Study 190-901 evaluable population excludes Study 190-901 subjects who enrolled to Study 190-203. Observations at age 0 are omitted. Further requirements correspond to the inclusion/exclusion criteria of Study 190-203 and a follow-up duration requirement to allow reliable estimation of ML rate of decline.

- At least one assessment ML ≥ 3
- At least two ML assessments in the range 1 – 6 and at least 6 months apart

4.2 Treatment Group Presentation

This is a single-arm study. Subjects < 2 years of age received lower than 300 mg dosing according to protocol and then received dosing of 300 mg after their 2nd birthday. Efficacy analyses will be for the full group of subjects, regardless of dose level received. Descriptive summaries of safety data will be provided by age category (separate columns) as well as full group (total column):

	BMN 190-203 Statistical Analysis Plan, Version 2.0	Pg. 16 of 53
---	---	--------------

- Baseline age < 2 years
- Baseline age < 3 years
- Baseline age \geq 3 years

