7.2 Previous Clinical Studies

BMN 190 has been studied in human clinical trials 190-201 and 190-202. Study 190-201 was a 48-week, international, multicenter phase 1/2 open-label dose-escalation study designed to assess the safety and efficacy of BMN 190 administered to patients with mild to moderate CLN2 disease by direct intracerebroventricular infusion to the CNS; Study 190-202 is the open-label extension of 190-201. These studies evaluated the safety, tolerability and efficacy of BMN 190 given as an infusion of 300 mg every 14 days given directly to the CNS using a permanently implanted intracerebroventricular (ICV) access device. A total of 24 patients with screening CLN2 motor-language scores ≥ 3 (0 to 6 point scale) and age ≥ 3 were enrolled into the 190-201 study. All completers without predefined stopping criteria were qualified to enroll into the long term extension, Study 190-202.

All patients had successful surgical implantation of ICV access devices, with device complication rates consistent with what has been observed in the published literature.

Interim results of the completed 48-week open-label study (190-201) and the ongoing extension study (190-202) have been published (Schulz, 2018). The primary outcome measure was the time until a 2-point decline in the score on the motor and language domains of the CLN2 Clinical Rating Scale (which ranges from 0 to 6, with 0 representing no function and 3 representing normal function in each of the two domains), which was compared with

BIOMARIN[®] 190-203 Amendment 6

the time until a 2-point decline in 42 historical controls. Additionally, rate of decline in motor–language score was compared between the two groups using data from baseline to the last assessment with a score of more than 0, divided by the length of follow-up (in units of 48 weeks).

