9.4.1 Treatments Administered

BMN 190 will be administered by ICV infusion every 14 days (\pm 3 days), preferably in the morning, according to the patient's age:

- birth to < 6 months: 100 mg
- 6 months to < 1 year: 150 mg
- 1 year to < 2 years: 200 mg (first 4 doses), 300 mg (subsequent doses)
- ≥ 2 years: 300 mg

BIOMARIN 190-2

190-203 Amendment 6

Patients younger than 2 years will start the study at the dose level appropriate for their age and will transition to the dose level consistent with their age as they mature.

Fasting for a minimum of 2 hours may be considered for the first infusion and subsequent infusions until the subject's reaction to the study drug is determined. When a feeding tube is used, the tube may be turned off 2 hours before infusion.

The normal infusion will be administered over 4 (± 1) hours at a rate of 2.5 mL/hr; the dose will be determined by the patient's age. Subjects not receiving the full 300 mg dose (administered in a total volume of 10 mL), will receive the appropriate volume at a rate of 2.5 mL/hr for over a shorter duration of time (see Table 9.4.1.1 below).

Age	Dose	Rate	Infusion Time	Dose Modification Options (AEs)
birth to < 6 months	100 mg	2.5 mL/hr	1.3 hours (±0.5 hr)	 Reduce infusion rate and administer drug over 2 hours Reduce the dose by 50% administered over the 1.3 (±0.5) hours Reduce the infusion rate and administer 50% of the target dose over 2 hours
6 months to < 1 year	150 mg	2.5 mL/hr	2 hours (±0.5 hr)	 Reduce infusion rate and administer drug over 3 hours Reduce the dose by 50% administered over the 2 (± 0.5) hours Reduce the infusion rate and administer 50% of the target dose over 3 hours
1 year to < 2 years	200 mg (first 4 doses),	2.5 mL/hr	2.7 hours (±1 hr)	• Reduce infusion rate and administer drug over 4 hours (200 mg); 6 hours (300 mg)
	300 mg (subsequent doses)	2.5 mL/hr	4 hours (±1 hr)	 Reduce the dose by 50% administered over the 2.7 (±1) hours (200 mg); 4 (±1) hours (300 mg) Reduce the infusion rate and administer 50% of the target dose over 4 hours (200 mg); 6 hours (300 mg)
≥2 years	300 mg	2.5 mL/hr	4 hours (±1 hr)	 Reduce infusion rate and administer drug over 6 hours Reduce the dose by 50% administered over the standard time of 4 (± 1) hours Reduce the infusion rate and administer 50% of the target dose over 6 hours

 Table 9.4.1.1: Age-Specific Dosing Schema for BMN 190 Administration

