9.4.4 Directions for Administration

Surgical implantation of an ICV reservoir will take place prior to study drug administration. The investigator will evaluate the patency, location, and skin integrity of the reservoir at each study drug administration (refer to the Study Pharmacy Manual). At each administration, the investigator will draw 1-2 ml of CSF into the device cannula to check for patency prior to administering the study drug. This volume of CSF is also to be used for laboratory testing (cell count, protein, glucose, and culture) as noted in Table 9.1.1. Access to the device is performed using strict sterile technique. Skin covering the reservoir is inspected for an appropriate needle insertion site. The needle insertion site must be intact, without evidence of breakdown, wound, infection or rash. The needle used is a small gauge non-boring tip. Once the reservoir has been accessed, the needle is immobilized to ensure minimal movement or risk of removal. If the needle dislodges during an infusion, it may not be reinserted, as sterility has been compromised. At the discretion of the investigator and/or neurosurgeon, the

BOMARIN

reservoir may be replaced during the clinical study. Refer to Section 7.4.2 for risks associated with the implantation procedure.

All study subjects will be administered BMN 190 by ICV infusion every 14 days (\pm 3 days), preferably in the morning. Fasting for a minimum of 2 hours may be considered for the first infusion and subsequent infusions until the subject's reaction to the study drug is determined. When a feeding tube is used, the tube may be turned off 2 hours before infusion. Study procedures for each study visit should precede study drug infusion unless otherwise specified. The date, time, volume, and concentration of each dose of study drug administered to each subject will be recorded in the dispensing log provided for the study as well as on the appropriate eCRF. The Study Pharmacy Manual provides further instructions on preparation and administration of study drug.

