11 COMPLIANCE

Measures of compliance will be summarized:

Actual study drug intake relative to planned study drug intake, expressed as a proportion:

$$100\% \times \frac{\text{Exposure (mg)}}{\text{Planned intake (mg)}}$$

Number (%) of missed infusions

Number (%) of infusions administered more than 3 days outside the target dosing day.

Number (%) of interrupted infusions

BIOMARIN®	BMN 190-203 Statistical Analysis Plan, Version 2.0	Pg. 25 of 53
------------------	---	--------------

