14.1.7 Adverse Events of Special Interest (AESI)

“Adverse events of special interest” (AESIs) are defined in the study protocol (Section 10.1.3) to include:

- Status epilepticus
- Status epilepticus is defined to comprise the following MedDRA preferred term: status epilepticus.
- Hydrocephalus (communicating and non-communicating)
- Hydrocephalus is defined to comprise the following MedDRA preferred terms: hydrocephalus, congenital hydrocephalus.
- Meningitis
- Meningitis is defined to comprise the MedDRA preferred terms presented in [Appendix 5](#).
- Unexpected rapid decline on CLN2 scale not attributable to other causes
- This will be identified by clinical review.
- Hypersensitivity (see Section 14.1.6)
- Temporally-related events (TRE) (e.g. AEs with onset after initiation of a study drug infusion and within 24 hours of the start or restart of the infusion)

	BMN 190-203 Statistical Analysis Plan, Version 2.0	Pg. 41 of 53
---	---	--------------

- Device-related events (e.g., infection, prophylactic ICV replacement, malfunction with an associated AE such as leaking reservoir or a problem that ends the administration of study drug for that visit, etc)
- Cardiac and ECG events

It is defined to comprise the preferred terms within the SOCs of vascular disorders and cardiac disorders, the High Level Term of ECG investigations, and the HLGT of cardiac and vascular investigations.

Adverse events of special interest will be summarized in a similar manner to general adverse events.

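### SAP 4.2 misstates dosing under 2 years and fixes safety columns by baseline age, so infusion-linked events cannot be tied to the dose given

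*SAP*

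**What the plan says.** SAP 4.2 (Treatment Group Presentation) states that subjects under 2 years "received lower than 300 mg dosing according to protocol and then received dosing of 300 mg after their 2nd birthday". It then sets the reporting rule for safety: "Descriptive summaries of safety data will be provided by age category (separate columns) as well as full group (total column"). The categories are baseline age under 2, under 3, and 3 years or older.

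Protocol 9.4.1 gives 100 mg from birth to under 6 months, 150 mg from 6 months to under 1 year, and then "1 year to < 2 years: 200 mg (first 4 doses), 300 mg (subsequent doses"). SAP 3.4 repeats this schedule. Protocol 9.4.1 adds that children move to the next dose as they grow older, and it allows dose changes for adverse events and, under 2 years, for PK results.

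SAP 14.1.7 defines temporally related events as "AEs with onset after initiation of a study drug infusion and within 24 hours of the start or restart of the infusion". It gives no breakdown by age or dose: "Adverse events of special interest will be summarized in a similar manner to general adverse events". Under SAP 14.1.1 that means incidence and number of events by system organ class, preferred term and severity. The age columns come from SAP 4.2 alone.

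**The concern.** Dose follows attained age and changes within a child, while the columns are fixed on the day of first dose. An event defined by the infusion it follows is therefore reported without the dose of that infusion. Because SAP 4.2 introduces the columns with a sentence implying reduced doses up to the second birthday, a reader could take the under-2 column as a reduced-dose group.

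This matters because safety and tolerability is a primary objective, and dosing at these ages is new to the programme: children with "age ≥ 3 were enrolled into the 190-201 study". Protocol 9.4.6 makes the 200 mg step a precaution, so that safety, tolerability and PK can be assessed before escalation. The SAP plans no safety output that reports on that step or on the lower infant doses.

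**Working it through.** **Texts side by side.** For a child aged 1 to under 2 years, SAP 4.2 implies no 300 mg infusion before the second birthday. SAP 3.4 and Protocol 9.4.1 imply 300 mg from the fifth infusion in that band. Both cannot be right, and Protocol 9.4.6 supports 300 mg down to 1 year of age.

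**Counting the infusions.** Neither document states a share of infusions by dose, so there is no figure to reproduce. Inputs and assumptions:

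- One infusion every 14 days for 144 weeks (SAP 3.4): 144/2 = 72 infusions, at days 14k after the first, k = 0 to 71.
- Month = 365.25/12 days. Dose is by age at infusion under SAP 3.4.
- Assumption: the four 200 mg doses also apply to a child who turns 1 on study.
- Start ages are assumed; the documents do not give them.

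Start at birth: 14k < 182.6 gives 14 infusions at 100 mg. 14k < 365.25 gives 27 before age 1, so 27 − 14 = 13 at 150 mg. Then 4 at 200 mg, leaving 72 − 31 = 41 at 300 mg (56.9%).

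| Age at first dose | 100 mg | 150 mg | 200 mg | 300 mg | Share at 300 mg |
|---|---|---|---|---|---|
| Birth | 14 | 13 | 4 | 41 | 57% |
| 3 months | 7 | 13 | 4 | 48 | 67% |
| 6 months | 0 | 14 | 4 | 54 | 75% |
| 9 months | 0 | 7 | 4 | 61 | 85% |
| 12 to 22 months | 0 | 0 | 4 | 68 | 94% |
| 23 months | 0 | 0 | 3 | 69 | 96% |

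Without the 200 mg step for children who turn 1 on study, the birth figure rises to 45/72 = 62.5%. With a 73rd infusion at Week 145 it is 42/73 = 57.5%.

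**Size of the SAP 4.2 error.** A 12-month starter has 27 infusions before the second birthday, of which 27 − 4 = 23 (85%) are 300 mg. An 18-month starter has 14, of which 10 (71%) are 300 mg. SAP 4.2 implies zero in both cases.

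**Dependence on follow-up.** From birth, the 300 mg share is 17/48 (35%) at 96 weeks and passes one half only at 126 weeks (32/63). From 6 months it is 18/36 (50%) at 72 weeks. From 12 months it is already 8/12 (67%) at 24 weeks.

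**Do other outputs fill the gap?**

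- Convulsions by 24-week interval (SAP 14.1.5): for a 12-month starter the first interval holds 12 infusions, 4 at 200 mg and 8 at 300 mg.
- Vital signs by visit (SAP 14.3) isolate early visits, but not dose.
- SAP 11 gives an overall "Number (%) of interrupted infusions", and SAP 12 gives exposure in mg. Neither is linked to events.
- SAP 14.1.3 and 14.1.4 list serious events and events causing discontinuation, without infusion denominators. No listing of non-serious temporally related events is specified.

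**The case against.** The best defence is that the sentence in SAP 4.2 is background text. The correct schedule stands in SAP 3.4, the columns are labelled by age and not dose, safety is descriptive, and serious cases are listed individually. Much of this stands. The sentence alone would be near-clerical, and that the column reads as a reduced-dose group is an inference.

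A reader might go further and infer that an excess at low doses would be diluted by later 300 mg infusions. The documents do not support that. The planned tables give incidence and event counts, and later infusions cannot lower either. What is lost is attribution to dose and a per-infusion denominator. A reader might also infer that infants face an infusion-rate hazard hidden by the grouping. Nothing in the documents shows the rate to be unsafe or that a child under 1 year was enrolled, and infusion rate is a design question separate from how tables are grouped.

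Two further objections stand as limits. The 300 mg majority assumes nearly full follow-up for the youngest starters. Changes made for adverse events or PK can also break the link between age and dose, so a table by age band alone would repeat the fault.

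None of this removes the gap. It exists even if every child started at 12 months or later, because it then concerns the four 200 mg doses.

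**Conclusion.** The point holds as a cheap improvement to safety reporting. SAP 4.2 contradicts SAP 3.4 and the protocol, and the baseline-age columns leave temporally related events without the dose they followed. Under the planned schedule and about 144 weeks of treatment, 57% (start at birth) to 94% or more (start at 12 months or later) of infusions in the under-2 column are 300 mg. Actual shares depend on start ages, completion and dose changes.

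The reduced-dose experience may be small. With the quota minimum of five children under 2, all starting at 12 to 22 months, 5 × 68 = 340 of 5 × 72 = 360 infusions (94%) are 300 mg, leaving 20 at 200 mg. No event in 20 infusions would still be compatible with a rate up to 1 − 0.05^(1/20) = 14% (one-sided 95% limit, infusions treated as independent). No test, error rate or efficacy result is affected.

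**What to change.** 1. **SAP 14.1.7:** add one descriptive table for subjects with baseline age under 2 years. Show temporally related events (including those that are hypersensitivity events) and interrupted infusions, by recorded dose at the infusion concerned (100, 150, 200, 300 mg) and by attained age. Show doses modified for adverse events or PK separately. Give numbers of infusions and subjects as denominators. State that dose, age and infusion number are confounded.
2. **SAP 4.2:** replace the dosing sentence with the SAP 3.4 schedule, for example: *Subjects under 2 years started at the dose for their age and moved to the next level as they aged; those aged 1 to under 2 years were scheduled for 200 mg for four doses and 300 mg from the fifth.*

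The cost is one sentence and one table. Protocol 9.4.4 already requires the inputs: "The date, time, volume, and concentration of each dose of study drug administered to each subject will be recorded". Identifying a temporally related event already requires its onset relative to the infusion, and SAP 4.6 already imputes incomplete birth dates. The downside is that some cells may be sparse or empty, and the table can only describe.

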4.3 Study Day Derivation

A study day will be obtained by subtracting the initial study drug start date from a visit date plus 1 if the visit date occurs after the initial study drug start date. Otherwise, the study day will be the visit date minus the initial study drug start date. Therefore, Study Day 1 will be the same date as the initial study drug start date.

For Study 190-901, the time of events is presented in terms of the subjects' age, in units of months. The Study 190-901 assessment that is used as a match to a Study 190-203 subject will be assigned as Study Day 1. Study Day is assigned to subsequent records assuming 30-day months, e.g., Study Day 31, 61, 91, etc.

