Twenty-four subjects were enrolled in Study 190-201/190-202, 23 of whom constituted the efficacy population. Interim efficacy results demonstrated a statistically significant and durable treatment effect in attenuating disease progression as measured by CLN2 scores and in comparison to natural history. Of the 24 patients enrolled into Study190-201, all but 2 subjects were in the active loss of function phase of the disease characterized by both notable disease burden and decline by a median value of 2 points per 48 weeks. In the 23 subjects who received BMN 190 for at least 96 weeks in Study 190-201/ 190-202, the median time until a 2-point decline in the motor–language score was not reached and was 345 days for historical controls. The mean (SD) unadjusted rate of decline in the motor–language score per 48-week period was 0.27 (0.35) points in treated subjects and 2.12 (0.98) points in 42 historical controls (mean difference, 1.85; P < 0.001). Common AEs included convulsions, pyrexia, vomiting, hypersensitivity reactions, and failure of the intraventricular device. In 2 subjects, infections developed in the intraventricular device that was used to administer the infusion, which required antibiotic treatment and device replacement.

PK analysis of ICV-delivered BMN 190 demonstrates concentrations and exposures that are three orders of magnitude greater in the CSF than in the plasma.

No association was found between ADA, including drug-specific IgE positivity, and incidence or severity of hypersensitivity adverse events.

Taken together, the response in the treated group is significant when compared to the loss of function predicted by natural history studies. The conclusions of treatment effect are constant across all analysis methodologies and sensitivity analyses. Most patients (87%) experience neurodegenerative stabilization, in which active decline in function is either halted (57%), has an early single point decline with no subsequent loss (22%) or actually improves function on treatment (9%).

In conclusion, BMN 190 via ICV infusion is generally safe and well tolerated. BMN 190 treatment demonstrated a durable and clinically meaningful therapeutic effect on attenuating disease progression compared to natural history.

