4.6 Handling of Dropouts and Missing Data

Missing ML assessments for symptomatic patients (baseline ML < 6 points) will not have much impact on the assessment of the primary endpoint since the disease progression on ML score is close to linear, estimation of rate of decline in ML is reliable for follow-up periods of greater than 6 months and all subjects had been followed > 6 months. Impact of missing ML assessments for asymptomatic subjects (baseline ML = 6 points) is also expected to be low since the follow-up of matched Study 190-901 subjects is limited to the length of follow-up of the Study 190-203 subject matched. Additional analyses will be conducted as appropriate to evaluate the impact of the COVID-19 pandemic on the study conduct and results, especially for the treatment effect as estimated in the trial.

BIOMARIN®	BMN 190-203 Statistical Analysis Plan, Version 2.0	Pg. 17 of 53
------------------	---	--------------

Statistical models for time-to-event analyses accommodate variable follow-up arising from staggered accrual or early study discontinuation, using an assumption of missing at random.

The CLN2 assessment schedule for Study 190-901 is not regular and does not generally match CLN2 assessment frequency in Study 190-203. Summaries of CLN2 score over a window grid would have highly variable N which is difficult to interpret. For this reason, interpolation will be used. Summaries of matched Study 190-203 and Study 190-901 CLN2 data will be based on data that has been imputed to the Study 203 visit target, using linear interpolation between Study 190-901 subject visits. Details are provided in [Appendix 4](#).

Partial or missing dates for adverse events and medications will be imputed conservatively by assignment to the earliest and latest possible dates for start and stop dates, respectively.

Some patients only have year of birth recorded as permitted by the site Institutional Review Board. Age in integer months is provided at each visit for Denver assessment. For subjects with incomplete date of birth provided, the date of birth will be imputed by back-calculation of birth date from the date of Denver assessment: (date of Denver) – round ((age in months) x (365.25/12)). For subjects with multiple Denver assessments, the average of the imputed date of births is used.

BIOMARIN®	BMN 190-203 Statistical Analysis Plan, Version 2.0	Pg. 18 of 53
------------------	---	--------------

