Appendix 2: Estimation of Rate of decline for a Subject

The rate of decline on ML is based on selecting a starting and ending ML assessment. For Study 190-203 and Study 190-901, the starting assessment is the baseline ML assessment and the ending assessment is the last ML score > 0 . Note that for Study 190-901, the baseline ML assessment is defined as the assessment of matching to the Study 190-203 subject.

The rate of decline is calculated as follows:

1. Determine the slope of the line connecting the two points:

$$\text{Slope} = \frac{(\text{Ending ML score}) - (\text{Starting ML score})}{(\text{Ending date}) - (\text{Starting date})}$$

2. Calculate the rate of decline as the negative of the line's slope, scaled to a 48-week time period:

$$\text{Rate of decline} = (-1) \times (48 \times 7) \times \text{Slope}$$

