Appendix 3: Matching of Study 190-901 and Study 190-203 Subjects

The population for the primary analysis is based on the ITT population and a 3-1 matching algorithm. This matching algorithm is based on maximizing the number of Study 190-203 subjects matched to Study 190-901 subjects and satisfying several criteria (baseline ML score equal, genome: equal number of common alleles, baseline age close and no more than 3 months apart). The data of Study 190-901 subjects will be restricted and includes the assessment at the age of the match as the baseline assessment. Duration of follow-up is measured with respect to this baseline. Follow-up assessments up to the largest duration that is less than or equal to the full follow-up duration of the matched 190-203 subject are included for the matched analysis. If this derived duration of follow-up for the Study 190-901 subject is not of duration 6 months or greater, then matching at this age of assessment will not be considered. For Study 190-901, where the first assessment of ML has the value 6, backwards imputation of the value 6 to earlier ages is allowed.

Distance is defined as the absolute value of the difference in baseline age for the potential match. Study 190-203 subjects are paired off from first through last and there are potentially 14 matched pairs. No Study 190-901 subject is matched more than once. To maximize the number of matched pairs, and overall low mean squared distance, at each pairing:

- Identify the Study 190-203 subject who has not yet been matched and has the least potential Study 190-901 candidates for pairing based on the requirement for equal baseline ML score, equal number of common alleles and distance ≤ 3 . If greater than one Study 190-203 subject is identified, break the tie by considering the number of potential Study 190-901 candidates for matching based on the requirement of distance ≤ 2 . Potentially, there are still ties and repeat as needed using distance criteria based on thresholds ≤ 1 and ≤ 0 .

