Appendix 4: Imputation of CLN2 Scores at Nominal Time points

To enable a descriptive assessment of CLN2 scores at common time points in which all subjects contribute to the descriptive statistics, each subject of the 190-203 and 190-901 studies will have their CLN2 scores imputed to those time points.

Nominal time points are Weeks 4, 8, 12, ... 144, 168 with corresponding target Analysis Days 29, 57, 85, ... 1009, 1177.

The imputed CLN2 value at each target Analysis Day is calculated by linear interpolation. If a target Analysis Day is not bracketed on both sides by CLN2 scores, but there is a single CLN2 assessment within 28 days, inclusive, of the target Analysis Day, then that single assessment is used for imputation (observation carried forward). The imputed data of the 190-901 subjects is truncated to have no longer follow-up than the corresponding imputed data for the Study 190-203 subject matched.

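### Control follow-up is converted at 30 days per month while the 48-week scaling uses real days, so non-zero control declines come out about 1.46% too steep

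*SAP*

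**What the plan says.** SAP section 4.3 runs two clocks. For Study 190-203, Study Day comes from calendar dates, counted from first dose. For Study 190-901, time is held as the child's "age, in units of months". The matching assessment becomes Study Day 1, and after that "Study Day is assigned to subsequent records assuming 30-day months, e.g., Study Day 31, 61, 91, etc".

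Appendix 2 applies one formula to both studies. It divides the change in ML score, from baseline to the last non-zero score, by the time between them, and then says: "Calculate the rate of decline as the negative of the line's slope, scaled to a 48-week time period". The multiplier is 48 x 7 = 336 days. Section 13.1.1 takes the treatment effect as the 190-901 mean rate against the 190-203 mean rate.

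Three other places depend on the same control time:

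- Appendix 4 sets its grid in real days: "Nominal time points are Weeks 4, 8, 12, ... 144, 168 with corresponding target Analysis Days 29, 57, 85, ... 1009, 1177". An unbracketed target can be filled when "there is a single CLN2 assessment within 28 days, inclusive, of the target Analysis Day".
- Appendix 3 limits control data to "Follow-up assessments up to the largest duration that is less than or equal to the full follow-up duration of the matched 190-203 subject", without giving the unit in which durations are compared.
- The Kaplan-Meier and Cox analyses of section 13.1.3 need event times for both groups.

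Section 4.6, which back-calculates incomplete birth dates from age at the Denver assessment, uses a different month length: "round ((age in months) x (365.25/12" (closing brackets omitted).

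**The concern.** The short month falls on the control group only. It shrinks the denominator of every control slope, while the treated slopes and the 336-day multiplier stay in real time. In a single-arm study the comparison with natural history relies on both groups being measured on the same scale. A scale error in one group does not average out with more patients. If controls decline on average, it moves the primary difference toward the drug.

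The same conversion dates control events early, shifts control scores against the Appendix 4 grid, and may move the Appendix 3 cap.

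**Working it through.** **Inputs.** 30 days per month (SAP 4.3); 336 days (Appendix 2); 365.25/12 (SAP 4.6); 14 potential matched pairs and 3-1 matching, so up to 14 x 3 = 42 controls (Appendix 3). The illustrative rates come from Study 190-201/202 (Protocol 7.2): 0.27 (SD 0.35) points per 48 weeks in treated children and "2.12 (0.98) points in 42 historical controls". They are not results of this trial.

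**1. The plan's own figures.** Study Day = 1 + 30m for m = 1, 2, 3 gives 31, 61, 91, as the SAP states.

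**2. Size of the scale error.** 365.25/12 = 30.4375.

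- Elapsed time: 1 - 30/30.4375 = 0.0144, so 1.44% too short.
- Rate: [336d/(30m)] / [336d/(30.4375m)] = 30.4375/30 = 1.01458, so 1.46% too steep. This holds for any score change d other than zero and any follow-up m.
- Example: 2 points lost over 12 months is 336 x 2/360 = 1.8667 under the 30-day rule and 336 x 2/365.25 = 1.8398 in calendar time.
- A zero slope stays zero. An improvement is also scaled up, which works in the opposite direction.

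**3. Bias in the primary difference.** Bias = 0.01458 x true mean control rate. The rates below are assumptions, since the documents give none for this matched set.

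| Control rate (points per 48 weeks) | Bias |
|---|---|
| 0.5 | +0.007 |
| 1.0 | +0.015 |
| 1.5 | +0.022 |
| 2.12 | +0.031 |

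If the 2.12 was itself computed with 30-day months, the bias is 2.12 - 2.12/1.01458 = 0.030.

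**4. Effect on the test.** Illustrative Welch t with 14 treated and 42 controls, ignoring unequal weights:

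- Calendar time: (2.12 - 0.27)/sqrt(0.35²/14 + 0.98²/42) = 1.85/0.178 = 10.40.
- Control mean and SD both multiplied by 1.01458: 1.881/0.180 = 10.47.
- With only 14 controls: 6.65 becomes 6.68.

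**5. Event times.** Control time is short by 182.6 - 180 = 2.6 days at 6 months, 365.25 - 360 = 5.25 days at 12 months, and 1095.75 - 1080 = 15.75 days at 36 months. Control events are therefore dated early. Sparse control visits date events late, so no net direction is claimed for Kaplan-Meier or Cox.

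**6. Appendix 4 grid.** Take a last control visit 38 months after the match, with a matched child who has data at Week 168 (Day 1177).

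- Calendar time: round(38 x 30.4375) + 1 = Day 1158, 19 days before the target, so the score is used.
- 30-day rule: 38 x 30 + 1 = Day 1141, 36 days before the target, so the control drops out.

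**7. Appendix 3 cap, if applied in days to whole-month ages.**

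- Treated follow-up of 1008 days (144 weeks): 1008/30 = 33.6 and 1008/30.4375 = 33.1. Both admit month 33, so there is no effect.
- Treated follow-up of 1176 days (168 weeks): 1176/30 = 39.2 and 1176/30.4375 = 38.6. Month 39 is admitted only under the 30-day rule.

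**The case against.** Appendix 2 refers to dates and never names Study Day, so its use in the control slopes is an inference. That is true. But 190-901 time exists only as age in months, and section 4.3 gives the only conversion. If another is used, the SAP does not state it, and the clarification is needed anyway.

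The 30-day month is a declared approximation, applied as stated, and 365.25/12 serves a different purpose in section 4.6. Both points are fair, but declaring the approximation does not remove its effect when one group is in 30-day months and the multiplier is in real days.

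The strongest objection is size. At the highest assumed rate the bias is 0.031 against a standard error of 0.178, about one-sixth of a standard error. The 2.12 comes from a study enrolling children aged 3 and over, whereas this trial seeks at least 5 children under 2, so the control rate here may be lower. This stands, and it limits how much the point matters.

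Control timing is also coarse. Protocol 11.1 describes Hamburg registry scoring in 6-month periods, and a single interval can differ from the average because real months vary. Coarseness adds noise but does not cancel a systematic shift. It does make the day-level examples in steps 6 and 7 illustrations only. They depend on particular visit times, and Appendix 4 is descriptive.

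Finally, the Sign test in section 13.1.2 is nearly immune, since a sign changes only when the two slopes already lie within about 1.46% of each other. That supports the direction of effect but does not correct the primary estimate.

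**Conclusion.** The concern holds. If the section 4.3 conversion feeds the Appendix 2 slopes, every non-zero control rate is overstated by 1.46%, and the primary difference is biased toward the drug whenever controls decline on average. Over assumed control rates of 0.5 to 2.12 points per 48 weeks the bias is 0.007 to 0.031. At effects like those in Study 190-201/202 it would be unlikely to change the conclusion. It should still be corrected, because it is systematic, alters the reported estimate and is avoidable. The consequences for Appendix 4 and the follow-up cap are possible rather than certain, and the cap effect depends on a unit the SAP does not give.

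**What to change.** In SAP section 4.3, define 190-901 Study Day as round((age in months - age at match) x 365.25/12) + 1, in line with section 4.6. State that this is the time used for the Appendix 2 slopes, the Appendix 3 follow-up cap, the time-to-event analyses and the Appendix 4 interpolation. State the unit in which the cap is applied.

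The cost is one line of text and code and a re-run of the matched analyses. If the cap is applied in days, check whether the matched set changes, because the 6-month minimum in Appendix 3 is judged on the capped follow-up. The estimated effect becomes slightly less favourable to the drug, so a late change of this kind could not be read as chosen to help it. The June 2020 SAP (section 3.3) has the same 30-day rule. Final control rates would therefore be about 1.4% lower than the interim ones for this reason alone, and the clinical study report should say so.
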